6.2.2 Formulation, Appearance, Packaging, and Labeling

Not applicable.

6.2.3 Product Storage and Stability

Not Applicable.

6.2.4 Preparation

Not Applicable.

6.3 Measures to Minimize Bias: Randomization and Blinding

Randomization

Participants will be assigned with equal probability to one of the two groups for each intervention TSR with and without CVPR versus LAVR with and without CVPR. Participants will be randomized after anesthesiologist clearance for both surgical approaches and prior to the preoperative visit. Every effort will be made to minimize the time between randomization and the surgery. Participant will have the opportunity to review the surgery detail with the surgeon during the preoperative visit. Separate randomization schedules will be generated by the DCC for each Clinical Site using a random permuted block design. The DCC will provide treatment allocations to the Clinical Sites using REDCap randomization feature.

Masking

The study surgeon is providing clinical care to enrolled participants, thus masking the surgeon to treatment allocation or participant symptoms is not practical or feasible, other than the allocation concealment prior to surgical randomization. Given the surgical procedure require a transvaginal or abdominal incision, it is clinically not possible to mask the participant or other research personnel. Every attempt will be made to keep the research coordinator blinded when assessing symptoms via questionnaires during follow up visits. The dynamic pelvic ultrasound image will be saved and re-evaluated in a blinded manner retrospectively to confirm the results of the initial reading.

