2.3.3. Assessment of Potential Risks and Benefits

We believe that the risks and benefits to the participants are balanced in this study design. Exam, questionnaires, and imaging used in the study are minimally invasive and part of routine urogynecology care. While standard risks of surgery apply to the surgical procedures, previous studies have demonstrated the safety of the two procedures. If participants in either treatment group develop new symptoms after surgery, treatment is available. Currently, patients with ODS receive treatment without follow-up that would allow sufficient assessment of the safety and efficacy of the surgical outcome, which could otherwise guide more effective clinical decisions.

3. Outcomes and Measurements

Primary Outcome: Compare surgical success or failure in female participants with moderate to severe OD symptoms, and rectal hypermobility diagnosed by ultrasound, who are randomized to minimally invasive transvaginal sacrospinous rectopexy versus laparoscopic abdominal ventral rectopexy at 24 months after surgery. The primary outcomes will be measured by:

1. The degree of rectal hypermobility measured via ultrasound (i.e. compression ratio).
 - a. "Compression ratio" will be calculated as a means to quantify the relative change in length of the rectovaginal septum (RVS), in other words the degree of hypermobility / sliding rectum, and is expressed as a percentage using the following formula: $CR = (RVS_r - RVS_v) / RVS_r * 100$, where RVS_r (Rectovaginal Septum) and RVS_v represent the RVS length at rest and Valsalva.

The criteria for surgical failure will be defined as follows:

1. A participant will be considered a surgical failure if:
 - a. Rectal hypermobility with compression ratio more than 20% is detected via ultrasound.
2. Otherwise, a participant will be considered a surgical "success".

Secondary Outcome:

- Compare efficacy and safety of the surgery measured by:
 1. Postoperative pain - Participants will complete the Pain Scale (67) and an assessment of pain medication use preoperatively, and then at 2 weeks and 2, 12, and 24 months postoperatively.
 2. Postoperative functional activity level – Participants will complete the Activity Assessment Scale (68) which measures functional activity preoperatively and then at 2 weeks and 2, 12, and 24 months postoperatively.

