Appendix A – SOP: MR Defecography

Appendix B – SOP: Dynamic Pelvic Ultrasound

Appendix C – SOP: Surgical Procedures

Appendix D – SOP: Study Assessments and Measurements

Appendix E – Schedule of Forms

PROD Trial
Research Standard Operating Procedure

SOP TITLE: MR Defecography	Version # 1
SOP NUMBER: PROD_SOP_1	Page 40 of 50

PURPOSE:

To describe expectations for completing MR Defecography for the PROD Trial.

PERSONNEL RESPONSIBLE:

Trained personnel at each study site.

PROCEDURES:

1. MR imaging will be in the supine position with hips and knees bent at 45° using a closed-configuration 1.5T magnet (Siemens, Magnetom Avanto) and a Synergy body phased-array coil.
 - a. As with routine dynamic pelvic floor MRI examinations performed at NorthShore University HealthSystem, intravenous contrast will not be used.
 - b. No bowel preparation or intraluminal contrast material will be administered.
2. Subjects will be instructed to empty their bladder three hours before the examination to result in a moderately full urinary bladder during MRI.
3. Static multiplanar images of the pelvis will be acquired for anatomic evaluation using a 3-mm slice thickness with a 0-mm gap, for sagittal and axial T2-weighted sequences (echo time, 105 milliseconds; repetition time, 3000 milliseconds).
 - a. These will be used to collect anatomical geometries for use in modeling.
4. The rectum will then be filled with 60 mL of ultrasound gel (1% Gd-DTPA-GEL-Mixture).
5. The pelvis will be visualized in three planes (transversal, coronal, sagittal, T1 and T2) to find the appropriate sagittal plane in which all relevant pelvic floor organs could be acquired during defecation.
6. The sequence will take ~36s at a frequency of one shot per 1.1 s (True Fast Imaging with Steady State Precession; TR: 1.8 ms, TE: 1.01 ms).
7. Slice thickness will be 6 mm (field of view: 300 mm x 270 mm, image matrix: 256 x 256).
8. During the examination, patients will be instructed via headphones to first relax and then to perform a squeeze maneuver.
 - a. This will be followed by instructions to perform straining and evacuation maneuvers with the goal of emptying the rectum as completely as possible.
9. For measurements, three anatomic measurements relating to rectal support will be recorded at rest, and then also at the moment of maximum evacuation, which will be defined as the image in which the posterior cul de sac makes its closest approach to the anorectal junction.

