 - a. The first measurement will be the straight distance between the posterior cul de sac and anorectal junction.
 - b. The second measurement will be the perpendicular distance between the cul de sac and the pubo-coccygeal line.
 - c. The third measurement will be the perpendicular distance between the anorectal junction and the pubo-coccygeal line.
10. The relative change in length of the straight distance between the posterior cul de sac and the anorectal junction (CDS to ARJ) as observed on MR defecography will be used to define a compression ratio, which will

again be calculated as a percentage using the following formula: $\text{Compression ratio} = 100 * (\text{CDS to ARJ length at rest} - \text{CDS to ARJ septum length at evacuate}) / \text{CDS to ARJ length at rest.}$

PROD Trial
Research Standard Operating Procedure

SOP TITLE: Dynamic Pelvic Ultrasound	Version # 1
SOP NUMBER: PROD_SOP_2	Page 42 of 50

PURPOSE:

To describe expectations for completing Dynamic Pelvic Ultrasound for the PROD Trial.

PERSONNEL RESPONSIBLE:

Trained investigators of the PROD Trial.

PROCEDURES:

- The ultrasound procedure will be performed and read by trained investigators, including Drs. [name] and [name] at NorthShore University HealthSystem and Drs. [name] and [name] at Weill Cornell Medical Center- New York Presbyterian.
 - o The dynamic pelvic ultrasound image will be saved and re-evaluated in a blinded manner retrospectively to confirm the results of the initial reading.
- The competency criteria for the ultrasound procedure will be performing three to five cases under the supervision of [name] [name] and/or [name] until achieving the following milestone:
 - o The physician was able to perform all aspects of the procedure safely and competently.
- The principal investigator of the study, [name] [name], will review the data quality of the ultrasound procedures for the first ten ultrasounds completed.

Dynamic Pelvic Ultrasound:

1. Imaging will be obtained at the time of the study visit using:
 - a. BK Medical bk3000 with
 - b. 3D X14L4 (9038) Endocavity Transducer (frequency range: 14-4 MHz, focal range: 3-60 mm)
2. All ultrasound studies will be performed in the office setting with the patient in the dorsal lithotomy position, with hips flexed and abducted.
3. No preparation will be required, and no rectal or vaginal contrast will be used.

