4. Patients will be instructed to arrive to the office with a partially full bladder, and to avoid excessive pressure on surrounding structures that might distort the anatomy, the probe will be inserted into the vagina in a neutral position.
5. 360 degree endovaginal ultrasound volumes and dynamic ultrasound videos will be saved for further analysis.
6. For measurements, the distance between the posterior cul de sac and anorectal junction (“rectovaginal septum length”) will be measured both at rest and during Valsalva straining efforts using a dynamic imaging protocol in the mid-sagittal plane, allowing posterior compartment structures to be visualized. It should be noted that for Valsalva straining efforts, patients will be instructed to relax their pelvic floor while increasing intra-abdominal pressure. All images will include the cul de sac apically and the levator plate/anorectal junction caudally in order to standardize framing of the anatomy, and the dynamic recording will be started with the patient at rest and captured for 5 seconds of Valsalva straining (see Figure 1 top left & right).

a. “Compression ratio” will be calculated as a means to quantify the relative change in length of the rectovaginal septum (RVS), in other words the degree of hypermobility / sliding rectum, and is expressed as a percentage using the following formula: $CR = (RVS_r - RVS_v) / RVS_r * 100$ where RVS_r (Rectovaginal Septum) and RVS_v represent the RVS length at rest and Valsalva.

[figure not shown]

Figure 1: 2D dynamic endovaginal posterior compartment ultrasound of a patient with obstructed defecation symptoms at rest (left image) and at strain (right image). Rendering of an aluminum can is used to illustrate the concept of the rectal compression seen above. LP: Levator Plate, RVS: Rectovaginal Septum

PROD Trial
Research Standard Operating Procedure

SOP TITLE: Surgical Procedures	Version # 1
SOP NUMBER: PROD_SOP_3	Page 44 of 50

PURPOSE:

To describe expectations for completing surgical procedures (Transvaginal Sacrospinous Rectopexy and Laparoscopic Abdominal Ventral Rectopexy) for the PROD Trial.

PERSONNEL RESPONSIBLE:

Investigators performing surgical procedures of the PROD Trial.

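### The primary endpoint appears to rest on an unmasked ultrasound reading: the blinded re-read only confirms it, and no rule covers readings on opposite sides of 20%

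*Combined protocol and SAP*

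**What the plan says.** **Endpoint.** Sections 3 and 8.1 define surgical failure as: "Rectal hypermobility with compression ratio more than 20% is detected via ultrasound". Section 9.4.2 analyses the 24-month compression ratio, with separate rules for retreatment and missing data. None of these sections says whose reading is used.

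**Initial reading.** Section 6.2.1 has all investigators performing the ultrasound. The ultrasound SOP (Appendix B) says: "The ultrasound procedure will be performed and read by trained investigators".

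**Masking.** Section 6.3 says masking the surgeon is not feasible, and of everyone else that "it is clinically not possible to mask the participant or other research personnel". The only staff masking attempted at follow-up concerns questionnaires: "Every attempt will be made to keep the research coordinator blinded when assessing symptoms via questionnaires during follow up visits".

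**Blinded re-read.** Section 6.3 says, and Appendix B repeats: "The dynamic pelvic ultrasound image will be saved and re-evaluated in a blinded manner retrospectively to confirm the results of the initial reading". Neither place describes the re-reader, what counts as confirmation, or what happens if the readings disagree.

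**What is stored and measured.** Appendix B says "360 degree endovaginal ultrasound volumes and dynamic ultrasound videos will be saved for further analysis", and that "the dynamic recording will be started with the patient at rest and captured for 5 seconds of Valsalva straining". It does not say which Valsalva frame is measured. The MR SOP (Appendix A) does define its frame, at maximum evacuation, "which will be defined as the image in which the posterior cul de sac makes its closest approach to the anorectal junction".

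**The concern.** The sole primary endpoint is a yes/no classification at a fixed cut. The hypothesis in Section 9.1 is that the transvaginal procedure is superior, and Section 2.1 says the lead centre's own division developed it. If the value of record is the investigators' reading, people who may know the arm set the result, and they have some latitude in choosing the frame. A blinded measurement of the same recording is planned, but as written it need not affect the analysis.

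If the two readings conflict and no rule exists, someone must choose between them after both are known. Unless that choice is masked, it is a second route for bias. It is not known whether the readers are also the operating surgeons, because the readers' names have been removed from the public text.

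**Working it through.** **Step 1: textual check.** The places that could name the reading of record or settle a disagreement are these.

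| Place | What it settles | Reading of record? | Rule for conflicting readings? |
|---|---|---|---|
| Sections 3 and 8.1 | 20% cut | No | No |
| Section 6.3 | Re-read confirms the initial reading | By implication only | No |
| Section 9.4.2, endpoint | 24-month ratio; retreatment; missing data | No | No |
| Section 9.4.2, sensitivity analysis | Dropouts and missing data | No | No |
| Appendix B | Same re-read wording; supervised training cases; quality review of the first ten scans | By implication only | No |

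The finding rests on this table. The arithmetic below only shows how sensitive the endpoint is.

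**Step 2: inputs.** From the documents: cut 20%; SD of the compression ratio 14.4, with mean 19.6% at 12 months (pilot series, 20 patients, single arm, Section 4.2); planned success 70% and 93%, 48 evaluable per arm, ICC 0.01, 16 patients per surgeon, two-sided 5% (Section 9.2). Assumed: normal compression ratios, the same SD in both arms, and reader differences of 2 or 5 points. The plan has no figure of its own on reader error to reproduce.

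**Step 3: how often a rule would be needed.** Let the two readings have the same mean and SD 14.4, with a purely random difference of SD *s*. Their correlation is ρ = 1 − s²/(2 × 14.4²), which is 0.990 for s = 2 and 0.940 for s = 5. The probability of falling on opposite sides of 20 is 2 × [Φ(k) − Φ₂(k, k; ρ)], with k = (20 − mean)/14.4.

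- 70% success: k = 0.5244, so the mean is 20 − 0.5244 × 14.4 = 12.45. Result: 3.86% (s = 2) or 9.67% (s = 5).
- 93% success: mean −1.25. Result: 1.49% or 3.70%. A negative mean shows that the normal model is rough here.
- Pilot 12-month mean of 19.6: 4.4% or 11.1%.

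| Scenario, 96 evaluable patients | s = 2 | s = 5 |
|---|---|---|
| Planned rates, 48 × (70% arm + 93% arm) | 2.6 | 6.4 |
| Both arms at 70%, 96 × the 70% figure | 3.7 | 9.3 |

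**Step 4: effect of a directional reading bias.** Let both arms truly have 70% success, and let the reading favour one arm by *d* points. Apparent success in that arm is Φ(0.5244 + d/14.4): 0.700, 0.746 and 0.808 for d = 0, 2 and 5. The table gives the probability of a significant result favouring that arm, by exact enumeration of two binomials with an unstratified Pearson chi-square test. For clustering, the design effect is 1 + 15 × 0.01 = 1.15 and 48/1.15 = 41.7, taken as 42 per arm.

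| Per arm | d = 0 | d = 2 | d = 5 |
|---|---|---|---|
| 48 | 2.6% | 7.5% | 23.4% |
| 42 | 2.5% | 6.9% | 21.3% |

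An equal shift in both arms leaves the 48-per-arm figure at 2.5% to 2.6%. Only a difference between arms does harm, and that is what masking the reader guards against.

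**The case against.** **The text does not say the unmasked reading counts.** The re-read is listed among the measures to minimise bias, and confirming could mean that no result is final until the blinded reader has verified it. This stands in part. What is certain is that the reading of record and the rule for conflicts are unspecified; that the unmasked value governs is the more natural reading, not a stated fact. Under either reading, a conflict has no prescribed resolution.

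**Section 9.4.1 defers implementation to an SAP written before database lock.** A rule could still be set there. But the deferral covers implementation of the analysis and does not commit to this point. Which measurement defines the primary endpoint should be fixed before the two sets of readings can be compared by arm.

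**Other controls exist.** Appendix B requires supervised training cases, reviews data quality for the first ten scans, and standardises image framing and the Valsalva instruction. These should reduce random error. None masks the reader or settles a conflict.

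**The illustration can overstate the problem.** At the planned rates the conflicts fall to 2.6 or 6.4 of 96, and purely random disagreement barely moves the comparison. The pilot mean of 19.6% implies only about 51% success, far from either planned rate, and the pilot's baseline mean was 45.5% whereas this trial requires more than 50%. Nothing in the documents supports a 2- or 5-point bias confined to one arm. All this stands, and no weight is put on those figures as estimates.

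**The developer's interest may be site-specific.** Nothing shows that readers at the second centre developed the technique. That is fair, and it narrows the motive without providing masking.

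**Conclusion.** The concern holds. Followed as written, the plan allows an unmasked reading to decide the sole primary endpoint of a superiority trial, and it gives no rule when the blinded reading disagrees about success or failure. This conclusion comes from the text and needs no numerical assumption.

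Its practical size is unknown because no reader-agreement data are given. Under the stated assumptions, a handful of patients would need the missing rule. A modest reading bias in favour of one arm could raise false-positive risk several-fold; at the larger assumed shift of 5 points it is roughly ninefold (23.4/2.6). These figures describe sensitivity to reading error. They do not show that bias will occur, and they do not measure the benefit of the remedy. The change should be made because it strengthens the primary endpoint at almost no cost. Sample size, power and significance level are unaffected.

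**What to change.** State the following in Sections 6.3 and 9.4.2 and in Appendix B.

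1. The blinded re-read of every saved 24-month recording supplies the compression ratio for the primary endpoint.
2. The re-reader is an existing study reader who neither operated on nor scanned that patient and is masked to arm and to the initial value. The re-reader works from the saved dynamic video and chooses the rest and Valsalva frames independently.
3. The site reading is used in the primary analysis only if the recording is unreadable, and otherwise in a sensitivity analysis.
4. Agreement between the readings is reported by arm, including the number of pairs on opposite sides of 20%.

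At minimum, name the reading of record and give a masked rule for conflicting pairs.

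State the limits too. A blinded re-read does not remove bias from unmasked image acquisition, coaching of the Valsalva effort or retreatment decisions. Masking is also incomplete if mesh can be seen on the image, which the documents do not address.

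The cost is a few sentences and assigning readers. The re-read sentence is not limited to a sample, so the work (up to 120 recordings, or 96 with the planned 20% dropout) appears to be planned already. The sites should confirm that an eligible reader is available for each patient. No new scans, visits or patients are needed.

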6.4 Study Intervention Compliance

Surgeons will comply with randomization assignments to the extent possible. Variations will be documented as protocol deviation and justification for allowing clinical decision-making to overrule randomized treatment assignment will be documented. Protocol deviations will be reviewed by both the IRB and the Data Safety Monitoring Board (DSMB).

6.5 Concomitant Therapy

No additional surgical procedures will be performed at the same time as the research procedure described in this protocol. If any additional procedures, unanticipated or incidental, are performed for medical necessity, they will be documented as protocol deviation and described fully to the IRB and DSMB.

6.5.1 Rescue Medicine

Not applicable.

7. Study Intervention Discontinuation and Participant Discontinuation/Withdrawal

7.1 Discontinuation of Study Intervention

Incomplete MR imaging does not mean discontinuation from the study, and remaining study procedures can be completed as indicated by the study protocol. Patient can withdraw from the study before surgery.

If a clinically significant finding is identified (including, but not limited to changes from baseline) after enrollment, the investigator or qualified designee will determine if any change in participant management is needed. Any new clinically relevant finding, occurring or discovered after obtaining informed consent, will be reported as an adverse event (AE).

7.2 Participant Discontinuation/ Withdrawal from the Study

Participants are free to withdraw from participation in the study at any time upon request.

An investigator may discontinue or withdraw a participant from the study for the following reasons:

- Pregnancy
- Significant study intervention non-compliance
- If any clinical adverse event (AE), laboratory abnormality, or other medical condition or situation occurs such that continued participation in the study would not be in the best interest of the participant
- Disease progression which requires discontinuation of the study intervention
- If the participant meets an exclusion criterion (either newly developed or not previously recognized) that precludes further study participation
- Participant unable to receive MRI or surgery for 3 months

The reason for participant discontinuation or withdrawal from the study will be recorded on the Case Report Form (CRF). Participants who sign the informed consent form and are randomized but do not receive the study intervention may be PROD Trial – v4 Mar 14 2024

replaced. Participants who sign the informed consent form, and are randomized and receive the study intervention, and subsequently withdraw, or are withdrawn or discontinued from the study, will not be replaced.

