5.2 Exclusion Criteria

An individual who meets any of the following criteria will be excluded from participation in this study:

1. Contraindication to abdominal (history of severe intrabdominal surgery) and transvaginal rectopexy in the opinion of the treating surgeon
2. History of previous surgery that included any type of surgery for rectal prolapse
3. Pelvic pain or dyspareunia due to levator ani spasm that would preclude a PMT program
4. Previous adverse reaction to synthetic mesh
5. Current cytotoxic chemotherapy or current or history of pelvic radiation therapy within 12 months
6. History of two inpatient hospitalizations for medical comorbidities in the previous 12 months

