9.2 Sample Size Determination

Based on our preliminary studies in literature (83-87), we assume an anatomic success rate in LAVR group is about 70% at 24 months. The investigators believe that a difference in success rates less than 25% will not change clinical practice, but also that the sample size should be large enough so that an observed difference in success rates of 20% would be significant; i.e., an inability to differentiate between the procedures will require an observed difference that is less than 20%.

The study will be individually randomized group-treatment trial (IRGT), which patients are randomized to surgical interventions through a common surgeon (88-90). There will be three surgeons performing each surgical treatment. The number of surgeons and patients will be the same in each clinical site. We anticipate an average of 16 individually randomized patients per surgeon in each treatment group. Outcomes for patients treated by the same surgeon tend to be more similar. We assume minimal variability, estimating a small intraclass correlation coefficient (ICC) of 0.01. The table below illustrates power to detect at least 23% difference between treatment groups with varying assumptions on ICC and dropout rates. A total of 96 patients (48 patients per group) would yield 86% power to differentiate between anatomical success rates of 70% and 93% assuming an ICC of 0.01 and a two-sided 5% level of significance. Projecting a 20% dropout/loss to follow up rate over 2 years, we anticipate recruiting and up to 120 total patients.

ICC	% Dropout	Total patients	Average patients per surgeon	Power
0.01	0	120	20	92%
	10	108	18	90%
	20	96	16	86%
0.02	0	120	20	90%
	10	108	18	87%
	20	96	16	83%
0.05	0	120	20	82%
	10	108	18	79%
	20	96	16	76%

Due to concerns that ICC is higher than expected or dropout rate is higher than 20% toward the end of 2-year follow-up, we calculated the sample size that would be needed for 87% power to differentiate between anatomical success rates of 70% and 95% (a difference of 25%) in treatment groups with a two-sided 5% level of significance. The required sample size is 39 per group, or 78 total patients.

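### Section 7.2 lets investigators withdraw women after surgery for reasons that may track the outcome, and nothing keeps them in follow-up to 24 months

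*Combined protocol and SAP*

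**What the plan says.** Section 7.2 lists reasons for which an investigator may withdraw a participant from the study. Three matter here: significant non-compliance with the intervention; "Disease progression which requires discontinuation of the study intervention"; and "If the participant meets an exclusion criterion (either newly developed or not previously recognized) that precludes further study participation". The list is not confined to the period before surgery. The same section says that women withdrawn after receiving the intervention are not replaced. No section says that a withdrawn woman continues with any visit.

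Other sections bear on what happens to her data:

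- **Section 5.2, exclusion 2:** "History of previous surgery that included any type of surgery for rectal prolapse".
- **Section 9.4.2:** the 24-month primary outcome is set to failure after retreatment. It is also set to failure when the 24-month ultrasound and POPQ results are missing and the last measurements met the failure definition (compression ratio above 20%). A sensitivity analysis for dropouts is promised, without named scenarios.
- **Section 9.4.3:** missing secondary outcomes are not imputed.
- **Section 9.3:** the mITT set keeps every randomized woman with one post-operative visit.
- **Section 6.3:** surgeons, participants and most research staff cannot be masked.

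On imaging, section 7.1 says "Incomplete MR imaging does not mean discontinuation from the study", while section 7.2 lists as a withdrawal reason "Participant unable to receive MRI or surgery for 3 months".

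**The concern.** Each rectopexy is done once. After it, there is no continuing treatment to stop or comply with, so leaving treatment and leaving the study are different events. Section 7.2 does not separate them. Its reasons are discretionary, are applied by people who know the arm, and could be related to how well the operation worked. If so, the women whose 24-month outcome goes missing are not a random subset, and the comparison of success rates is biased. A rule in the analysis section can assign values to such women, but it cannot recover an ultrasound that was never done.

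The primary comparison, the 24-month symptom endpoint and the quality-of-life endpoints are all exposed. The last two are more so, because no imputation applies to them.

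**Working it through.** **1. The plan's own figure.** Section 9.2 needs 96 evaluable women and projects 20% dropout: 96 / (1 - 0.20) = 120, or 60 per arm. This reproduces exactly, and nothing below changes it. The planning success rates come from the same section: "anatomical success rates of 70% and 93% assuming an ICC of 0.01 and a two-sided 5% level of significance".

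**2. What section 9.4.2 catches.**

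| Woman withdrawn after surgery | Primary outcome |
|---|---|
| Retreated, and this is known | Failure |
| 24-month ultrasound and POPQ missing, last measurements failing | Failure |
| Last ratio 20% or less | No rule stated |
| No post-operative ultrasound (the first is at 2 months, section 1.3) | No rule stated |
| Retreated after exit | Not known to the trial |

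On the last row, section 8.3.4 ends event recording 7 days (non-serious) or 30 days (serious) after the last day of participation. A later repeat operation has no stated route into the database.

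**3. Is an early success informative?** In the investigators' 20-patient series of the transvaginal operation (section 4.2), the mean ratio was 9.2% (SD 13.7) at 2 months and 19.6% (SD 14.4) at 12 months. Under a normal approximation:

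- 2 months: z = (20 - 9.2) / 13.7 = 0.79, so about 22% exceed 20%.
- 12 months: z = (20 - 19.6) / 14.4 = 0.03, so about 49% exceed 20%.

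The approximation is rough, since the 2-month SD exceeds the mean, but the rise in the mean does not depend on it. A ratio of 20% or less at 2 months says little about 24 months.

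**4. Bias if failures escape.** Let p be true success and e the share of an arm's failures that leave the denominator unrecorded. Then apparent success = p / (1 - (1 - p)e). Here e = (share of failures withdrawn) x (share of those that section 9.4.2 does not catch). The documents give neither share. I assume 25-50% for each, so e runs from 0.25 x 0.25 = 0.0625 to 0.50 x 0.50 = 0.25. At p = 0.70 and 60 women there are 18 failures, so this means 1.1 to 4.5 women.

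- e = 0.0625: 0.70 / (1 - 0.01875) = 71.3%, up 1.3 points.
- e = 0.125: 0.70 / (1 - 0.0375) = 72.7%, up 2.7 points.
- e = 0.25: 0.70 / (1 - 0.075) = 75.7%, up 5.7 points.
- e = 0: 70.0%. This is the result if every withdrawn failure is caught or followed.

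**5. Direction.** With e = 0.25 in both arms, the 93% arm becomes 0.93 / (1 - 0.0175) = 94.7%, and the difference falls from 23 to 94.7 - 75.7 = 19.0 points. With e = 0.25 in the 70% arm only, it falls to 93 - 75.7 = 17.3. In the 93% arm only, it rises to 94.7 - 70 = 24.7.

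**6. False positives.** Suppose both arms truly have 70% success, failures escape in one arm only, and a pooled two-sided z-test is used on 60 per arm with clustering ignored. Rejection is 5.0% at e = 0, 5.8% at e = 0.10 and 10.4% at e = 0.25.

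**The case against.** The strongest defence is section 9.4.2. A reader might infer that retreatment meets exclusion 2, so retreated women are withdrawn and their failures vanish. The documents do not support that for the primary endpoint. A woman withdrawn because she was retreated is known to be retreated, section 7.2 has the reason recorded, and she is scored as a failure. Exclusion 2 also covers only surgery for rectal prolapse, and a newly met criterion counts only if it precludes further participation. This objection stands and removes the retreatment route, except for retreatment after exit.

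A reader might also equate disease progression with recurrence. The text limits it to progression that requires stopping the intervention. Read literally, that could hardly apply after a single operation, and section 10.1.1.1 describes managing surgical failures, not withdrawing them. This stands in part. The wording is unclear rather than plainly wrong, but section 7.2 does foresee withdrawal after surgery and does not say which reasons then apply.

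The mITT definition and the sensitivity analysis help less. The first keeps a woman in the set without giving her an outcome. The second has no stated scenarios. Section 9.4.1 leaves implementation to a later SAP, which could add a rule but not the missing measurement.

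Finally, a reader might infer that the MRI clause costs primary data. It does not for treated women: the Schedule of Activities places MR defecography before randomization and does not repeat it. Incomplete imaging and being unable to have imaging are also not quite the same thing.

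**Conclusion.** The point holds in a limited form. Section 7.2 permits withdrawal after surgery for reasons that may be related to outcome, and no section secures follow-up to 24 months. What remains after section 9.4.2 is women withdrawn with a last ratio of 20% or less or no post-operative ultrasound, unrecorded retreatment after exit, and the secondary endpoints.

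Under the assumed shares, one arm's apparent success is inflated by 1.3 to 5.7 points, against a planned difference of 23. This rests on three assumptions: e lies between 0.06 and 0.25, only failures escape, and women without an outcome leave the denominator. It would be zero if all withdrawn failures were caught. It would be wrong to say that the gap favours either operation. The difference can shrink or grow, depending on which arm loses failures. The effect on secondary endpoints cannot be sized from the documents.

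This should be changed, because the repair is simple and missing ultrasounds cannot be recovered later. The MRI wording is a minor, separate matter.

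**What to change.** - **Section 7.2:** state that, for women who have had surgery, non-compliance, disease progression and a newly met exclusion criterion are not reasons to end follow-up. Unless consent is withdrawn, the 24-month ultrasound, the questionnaires and any retreatment are still recorded.
- **Section 9.4.2 or the SAP:** state the primary-analysis rule for a woman without a 24-month ultrasound whose last ratio was 20% or less or who has no post-operative ultrasound. Name the sensitivity scenarios for these women.
- **Pregnancy and safety:** management stays as the protocol (section 8.3.9 for pregnancy) and clinicians decide. Whatever outcome data are available should be recorded.
- **Minor:** reconcile the MRI wording of sections 7.1 and 7.2. This concerns women before randomization.

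The cost is a protocol amendment and a few lines in the SAP. The visits are already in the Schedule of Activities, and the sample size of 120 is unchanged.
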